Appendix 1.2. Further Definition of Endpoints75

Appendix 2. SCHEDULE OF ACTIVITIES77

1. AMENDMENTS FROM PREVIOUS VERSION(S)

1.1. Changes from Version 1.1 to Version 2.0

This amendment to the SAP is the second amendment to the original approved SAP (version 1 dated 24October2013). This amendment was initiated after the finalization of Amendment 2 to Protocol B1481022 (dated 12February2016), and further revised due to the discontinuation of the bococizumab clinical development program on 01November2016, and finalized prior to sponsor unblinding. Six unblinded DMC reviews have been conducted, all with recommendations to continue the study without modification.

Summary of changes of this amendment versus the previously amended SAP (Version 1.1 on 12November2014) include:

Changes to the SAP driven by changes to the protocol:

- Visit dates in months were replaced by visit dates in weeks throughout the SAP.
- Italicized text from the Protocol Amendment 1 was replaced with italicized text from Protocol Amendment 2 in Sections 2 – 6 and in Appendix 1.2 and Appendix 2. Italicized text from Protocol Amendment 1 in Sections 7 - 8 was replaced with normal text from Protocol Amendment 2.
- Corresponding to the change in entrance criteria, a randomization stratification factor for LDL-C at the pre-screening visit (<100 mg/dL, ≥ 100 mg/dL) was added (Sections 2.1 and 6.4).
 - LDL-C at the pre-screening visit (<100 mg/dL, ≥ 100 mg/dL) was added as a stratification factor for stratified log rank tests and Cox proportional hazards model (Sections 8.1.1.1, 8.2.1, 8.2.2, and 8.2.4), a covariate for the multiple imputation model (Section 8.2.1), and as a factor to all MMRM and ANCOVA models (Sections 8.1.1.2, and 8.2.2).
- The number of primary endpoint events required for stopping the trial in certain subgroups, including diabetic subjects with no prior CVD event, was corrected to 58 (Section 2.1), the probability of a point estimate of the hazard ratio being less than 1 within these subgroups was corrected to 80% (Sections 2.1 and 3).
- In response to changes in the objectives and endpoints:
 - The composite endpoint of all-cause death, non-fatal MI and non-fatal stroke was upgraded to a key secondary objective from other secondary objective (Section 2.2), the corresponding endpoint was elevated to a key secondary endpoint (Section 6.1.2) and the corresponding analysis was elevated to a key secondary analysis (Section 4.2).

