Restricted Maximum Likelihood (REML) estimation will be used, and the default covariance structure will be unstructured. Due to the slow onset of accrual in this event-driven trial, there will be few observations at the last several time points. One or more of the last visits may be removed to ensure convergence of the model fitting. Also, the geographic region with the fewest observations may be combined with the next smallest region to ensure convergence of the model fitting. This may be done twice. If the model fails to converge with an unstructured covariance matrix, a spatial power covariance will be used. If the model fails to converge with this covariance structure, compound symmetry will be used. Kenward-Roger degrees of freedom will be used. Consistent with MMRM model fitting, no explicit imputation of missing assessments will be performed. Estimates of treatment group means and mean treatment group differences using observed margins at Week 14 and each other visit, corresponding 95% confidence intervals, and p-values for the mean differences will be provided. The least-squares mean treatment group estimates and 95% confidence intervals will be plotted longitudinally as indicated below with an asterisk (*).

For nominal changes from baseline in Lp(a), triglycerides and hs-CRP, the same model will be fit in the same manner for log-transformed data. The data will be log transformed prior to calculating changes. Any zero values will be replaced with 0.0001 to enable taking the logarithm. The estimated treatment group means and corresponding 95% confidence intervals from the analysis of the log-transformed data will be transformed to percent changes for reporting. The estimated treatment group differences will be transformed to the ratio of the mean percent changes and reported with transformed 95% confidence intervals along with untransformed p-values.

The percent changes from baseline to last non-missing post-baseline measurement in LDL-C will be analyzed using an analysis of covariance model with treatment group and baseline value as covariates and geographic region and LDL-C at the pre-screening visit (<100 mg/dL, ≥100 mg/dL) as factors. Least squares means with corresponding 95% confidence intervals, the least-squares mean differences and corresponding 95% confidence intervals, and p-values will be presented. This analysis will not use analysis windows.

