8.2.4.1. Pharmacokinetic/Pharmacodynamic/Immunogenicity Reporting

Only plasma samples for all bococizumab-treated subjects will be tested for immunogenicity; plasma samples for placebo-treated subjects will not be tested. Only ADA positive samples will be tested for nAb.

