8.2.4.1.1. Definitions

ADA and nAb titers are provided to Pfizer in log₂ format and will be reported in the same manner. All titles and labels used in tables and figures should clearly indicate titer (log₂).

ADA Measurement Level Status:

An ADA measurement is considered as ADA positive if the ADA titer ≥ 6.23 ; otherwise if non-missing, the measurement is considered as ADA negative.

nAb Measurement Level Status:

An nAb measurement is considered as nAb positive if the nAb titer ≥ 1.58 (Assay #2). An nAb measurement is considered as nAb negative if the ADA measurement from that sample is negative or if the nAb titer < 1.58 .

ADA Subject Level Status – For subject level classification of ADA (positive, negative):

A subject will be considered ADA positive if:

- The subject is ADA negative at baseline and has at least 1 ADA positive post-dose measurement, or
- The subject is missing the baseline ADA measurement and has at least 1 ADA positive post-dose measurement, or
- The subject is ADA positive at baseline and has a >1.58 unit increase in ADA titer from a positive baseline titer in at least 1 post-dose measurement.

A subject will be considered ADA negative if:

- The subject is ADA negative at baseline and all post-dose measurements are negative, or
- The subject is missing the baseline ADA measurement and all post-dose measurements are negative, or
- The subject is ADA positive at baseline but does not experience >1.58 unit increase in titer from a positive baseline titer in any post-dose measurement.

nAb Subject Level Status – For subject level classification for nAb (positive or negative):

A subject will be considered nAb positive if:

- The subject is nAb negative at baseline and has at least 1 nAb positive post-dose measurement, or
- The subject is missing the baseline nAb measurement and has at least 1 nAb positive post-dose measurement, or

- The subject is nAb positive at baseline and has a >1.58 unit increase in nAb titer from a positive baseline titer in at least 1 post-dose measurement.

A subject will be considered nAb negative if:

- The subject is ADA negative, or
- The subject is nAb negative at baseline and all post-dose measurements are nAb negative, or
- The subject is nAb positive at baseline but does not experience a >1.58 unit increase in titer from a positive baseline titer in any post-dose measurement.

ADA (nAb) Response Type:

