ADA (nAb) positive subjects will further be classified according to the type of ADA (nAb) response (treatment induced/treatment boosted/indeterminate):

A subject will be considered as having treatment induced ADAs (nAbs) if:

- The subject is ADA (nAb) negative at baseline with at least 1 ADA (nAb) positive post-dose measurement, or
- The subject's baseline ADA (nAb) sample is missing with an ADA (nAb) negative post-dose measurement followed by at least 1 ADA (nAb) positive post-dose measurement.

A subject will be considered as having indeterminate ADAs (nAbs) if:

- The subject's baseline ADA (nAb) sample is missing with at least 1 ADA (nAb) positive post-dose measurement that was not preceded by an ADA (nAb) negative post-dose sample.

A subject will be considered as having treatment boosted ADAs (nAbs) if:

- The subject's baseline sample was ADA (nAb) positive with an increase in ADA (nAb) titer of >1.58 unit increase in titer from a positive baseline titer in at least 1 post-dose measurement.

Timing of ADA (nAb) Positive Measurement:

ADA (nAb) positive subjects will also be classified according to the timing of the ADA (nAb) positive measurement with respect to last dose of bococizumab (on treatment/off treatment):

A subject will be considered as having on-treatment ADAs (nAbs) if:

- The subject has any ADA (nAb) detected within ≤ 14 days after last dose.

A subject will be considered as having off-treatment ADAs (nAbs) if:

- The subject has their first ADA (nAb) detected >14 days after last dose.

Duration of ADA (nAb) Response:

ADA (nAb) positive subjects will also be classified according to the duration of ADA (nAb) response (indeterminate/persistent/transient) if the date of the first post-baseline measurement to the date of the last post-baseline measurement is at least 16 weeks:

A subject will be considered as having indeterminate duration of ADAs (nAbs) if:

- The subject has a positive ADA (or nAb) detected at the last post-baseline time point only.

A subject will be considered as having persistent duration of ADA (nAb) if:

- The subject has positive ADA (or nAb) detected at all post-baseline samples assayed during any period of at least 16 weeks.

A subject will be considered as having transient duration of ADA (nAb) if:

- The subject has been classified as neither persistent nor indeterminate.

ADA (nAb) titer response:

Subjects will also be classified according to their maximum ADA (nAb) titer as

- ADA (nAb) negative,

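### The SAP's residual class for antibody duration can label a subject transient who never reverted, when the final EDC/EOS sample falls less than 16 weeks after a first positive

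*SAP*

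**What the plan says.** The duration rule in SAP 8.2.4.1.1 applies to ADA-positive and nAb-positive subjects, and only "if the date of the first post-baseline measurement to the date of the last post-baseline measurement is at least 16 weeks". That eligibility interval therefore has named ends. Three classes follow:

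- Persistent: "The subject has positive ADA (or nAb) detected at all post-baseline samples assayed during any period of at least 16 weeks".
- Indeterminate: "The subject has a positive ADA (or nAb) detected at the last post-baseline time point only".
- Transient: "The subject has been classified as neither persistent nor indeterminate".

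The persistent rule names neither the dates that bound its period nor a minimum number of positive samples. The transient rule does not ask for a return to negative.

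Protocol 6.4.2 to 6.4.4 place post-baseline ADA samples at Visits 6, 8, 10, 12, 14, 17 and 20 (Weeks 4, 14, 40, 70, 104, 156 and 208) and at EDC or EOS. The visit-window text in the protocol's Schedule of Activities gives EDC/EOS visits no window.

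The classes are used in SAP 8.2.4.2 (tabulation and subject listing) and SAP 8.2.4.3 (LDL-C summaries and box plots of percent change by duration class).

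**The concern.** A reader of a table or plot will take *transient* to mean that the antibody appeared and then went away. The rule does not guarantee this. A subject whose positivity began late and was still present at the last sample can land in the same class as a subject who reverted. Such a subject's duration is simply unknown, which is what *indeterminate* should convey.

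The situation is plausible in this trial. SAP 1.1 says that the plan was "further revised due to the discontinuation of the bococizumab clinical development program on 01November2016", and protocol Section 3 asks for EOS procedures in all randomized subjects. The EOS sample then falls wherever each subject happens to be in the schedule, so a short final interval can arise.

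At stake is the comparison of LDL-C response between persistent and transient antibody. Subjects with ongoing antibody would sit in the transient group. In addition, because the persistent period is not bounded by named dates, two programmers could follow the text and produce different tables.

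**Working it through.** **Inputs.** Scheduled ADA samples are at Weeks 4, 14, 40, 70, 104, 156 and 208, so the gaps are 10, 26, 30, 34, 52 and 52 weeks. The thresholds are 16 weeks for eligibility and 16 weeks for persistence. From the first protocol version (26 August 2013) to the program stop (01 November 2016) is 1,163 days, or 1,163 / 7 = 166.1 weeks. The Week 208 schedule is therefore out of reach and Week 156 scarcely reachable, and the SAP itself expects that "Due to the slow onset of accrual in this event-driven trial, there will be few observations at the last several time points". The EOS weeks below are assumptions chosen to illustrate.

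**Reading used.** Persistent if (date of last positive) − (date of first positive) ≥ 16 weeks within an unbroken run of positives.

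**Worked case: Week 4 negative, 14 negative, 40 positive, EOS 52 positive.**
1. Eligible? 52 − 4 = 48 weeks, at least 16: yes.
2. Persistent? 52 − 40 = 12 weeks, below 16: no.
3. Indeterminate? Two samples are positive, so not the last time point alone: no.
4. Transient by remainder, although no negative follows a positive.

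The label turns on EOS timing alone. With a first positive at Week 40, EOS at Week 55 (15 weeks) gives transient and EOS at Week 56 (16 weeks) gives persistent.

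**Enumeration.** With k samples there are 2^k − 1 patterns that contain at least one positive. Counts are persistent/transient/indeterminate.

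| Samples (weeks) | Patterns | Current rule | With the fix | Never reverted but transient |
|---|---|---|---|---|
| 4, 14, EOS 26 | 7 | 1/5/1 | 1/4/2 | 1 (−,+,+) |
| 4, 14, 40, EOS 52 | 15 | 4/10/1 | 4/9/2 | 1 (−,−,+,+) |
| 4, 14, 40, 70, EOS 80 | 31 | 12/18/1 | 12/17/2 | 1 (−,−,−,+,+) |
| 4, 14, 40, 70, 104, EOS 115 | 63 | 32/30/1 | 32/29/2 | 1 (−,−,−,−,+,+) |
| 4, 14, 40, 70, 104 (scheduled only) | 31 | 16/14/1 | 16/14/1 | 0 |

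Scheduled visits alone give none, because every scheduled gap after Week 14 is at least 26 weeks. Two consecutive positives from Week 14 on therefore always meet the 16 weeks.

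**The unbounded period.** If any 16-week window holding at least one sample, all positive, is enough, an isolated Week 40 positive between negatives at Weeks 14 and 70 qualifies as persistent: 70 − 14 = 56 weeks contain no other sample. This literal reading and the run reading disagree on 8 of 15 patterns (EOS 52) and 13 of 31 (Weeks 4 to 104). The two readings are alternatives, so their effects do not add.

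These are counts of patterns, not of subjects.

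**The case against.** The best defence is that the rule is deterministic and the label conventional. Transient is openly a residual class, and the SAP nowhere says that it means reversion. The pattern needs a first positive at the last scheduled sample, a positive final sample within 16 weeks, and nothing positive before. An EDC sample produces it only if no later sample follows, and subjects who continue after EDC are also to complete EOS. The planned listings show titers, status and duration class by subject, so a reader could reclassify. All of this is correct. It limits the size of the problem, but the tables and plots would still show a never-reverted subject as transient.

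Three stronger readings are tempting and are not supported:

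- *The SAP never says how 16 weeks is measured.* It does for eligibility, date to date. Only the persistent rule lacks named ends, and the eligibility wording makes first to last positive the natural reading of it.
- *An isolated positive will be reported as persistent.* The text allows this only if read literally, and that reading defeats the purpose of the class. Under the run reading a single positive spans zero weeks, so persistent and indeterminate do not overlap either.
- *The handling of ADA-negative samples for nAb is undefined.* It is defined: "An nAb measurement is considered as nAb negative if the ADA measurement from that sample is negative". What remains is a tension of wording, because "Only ADA positive samples will be tested for nAb" while the persistent rule speaks of samples assayed. Skipping such samples would go against the stated definition.

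**Conclusion.** The point holds in a narrow form, and its severity is minor. On the natural reading of the persistent rule, one pattern per EOS schedule is labelled transient without any reversion, and none is on scheduled visits alone. This assumes one EDC/EOS sample after the last scheduled sample, no missed samples, and visits on their nominal weeks. The number of subjects is unknown and cannot be derived from the documents. Separately, the persistent rule should name its bounding dates and a minimum number of positives.

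A reader might infer that the trial's conclusions on efficacy or on antibody effect are in doubt. They are not. No hypothesis test uses these classes, and the LDL-C summaries by ADA or nAb status, pre-existing ADA and titer tertile do not depend on them.

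**What to change.** Keep the 16-week eligibility condition and apply three exclusive classes in this order:

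1. Persistent: an unbroken run of at least two consecutive positive samples whose first and last dates are at least 16 weeks apart.
2. Indeterminate: not persistent, positive at the last sample, and no negative after the first positive.
3. Transient: all others, so that at least one negative follows a positive.

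State the convention that a subject who reverted and is positive again at the end, without a 16-week run, stays transient (4 of 15 patterns at EOS 52), as now. As a wording note, say in the duration rule that ADA-negative samples count as nAb negative, in line with the measurement-level definition.

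The cost is SAP wording and derivation code only. Relative to the run reading, one pattern per EOS schedule moves from transient to indeterminate, so that class becomes slightly larger. Patterns on scheduled visits do not change.

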8.2.4.2. Summarization of ADA and nAb Results

1. The number of samples analyzed for ADA and nAb will be summarized.
2. ADA and nAb results will be summarized as categorical endpoints by visit and overall incidence at the subject level. The numbers and percentages of ADA positive and nAb positive subjects will be classified according to (1) timing of result with respect to bococizumab dosing (on treatment/off treatment), (2) characterization of ADA and nAb response (treatment induced/treatment boosted/indeterminate), and (3) duration of ADA and nAb response (indeterminate/persistent/transient) using the definitions in [Section 8.2.4.1.1](#) will be presented. The summary of nAb status will be performed with two different denominators: number of subjects with non-missing ADA samples and number of ADA positive subjects.

3. ADA titers for ADA positive subjects and nAb titers for nAb positive subjects will be summarized by visit as continuous endpoints. Boxplots of ADA titer and nAb titer over time will be presented for ADA positive subjects and nAb positive subjects, respectively.
4. Time to first positive ADA result and time to first positive nAb result will be summarized as continuous endpoints in subjects who are ADA positive or nAb positive, respectively.

A listing will also be provided that details subject identifier, treatment group, ADA titer, ADA status, nAb titer, nAb status, ADA induction type, nAb induction type, duration of ADA response, duration of nAb response, relative days to first positive ADA detection, relative days to first positive nAb detection, and day on study.

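### For treatment-boosted subjects, the SAP's onset, timing and duration rules drop the titer rise that made them positive, so a late or brief boost can be recorded as an early, persistent response

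*SAP*

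**What the plan says.** SAP 8.2.4.1.1 works on two levels. Each sample is judged against a fixed cut-off: "An ADA measurement is considered as ADA positive if the ADA titer ≥ 6.23". The nAb rule has the same form, with a cut-off of 1.58. A subject who is already positive before dosing must meet a further condition to count as positive: "The subject is ADA positive at baseline and has a >1.58 unit increase in ADA titer". Without that rise the subject is ADA negative. With it, the response type is treatment boosted: "The subject's baseline sample was ADA (nAb) positive with an increase in ADA (nAb) titer of >1.58 unit increase".

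Three descriptors are then derived for subjects classed as positive:

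- **Timing.** On-treatment means "The subject has any ADA (nAb) detected within ≤ 14 days after last dose". Off-treatment means that the first detection comes later than that.
- **Duration.** Persistent means "The subject has positive ADA (or nAb) detected at all post-baseline samples assayed during any period of at least 16 weeks". Indeterminate means positive at the last post-baseline time point only, and transient is everything else.
- **Onset.** SAP 8.2.4.2: "Time to first positive ADA result and time to first positive nAb result will be summarized as continuous endpoints in subjects who are ADA positive", with the matching statement for nAb.

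SAP 5.4.2.5 repeats the onset summary, and SAP 8.2.3 repeats both onset and timing. SAP 8.2.4.3 splits LDL-C summaries and box plots by the duration class.

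**The concern.** The subject-level rule decides that detectable antibody in a baseline-positive subject is not in itself a response to treatment; only a rise is. The three descriptors drop that decision and ask only whether a sample is above the cut-off. Samples still at the baseline titer, which did not count when the subject's status was set, then count towards onset, timing and duration once one sample elsewhere is boosted.

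Nothing in the SAP limits the descriptors to boosted samples, removes boosted subjects from them, splits onset by response type, or says whether the baseline sample can be the first positive. SAP 5.4.2.4 and 8.2.3 refer to Section 6.2 for definitions, but that section holds none of these.

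At stake is the description of immunogenicity, which is a stated safety objective. An onset table could show early responses that were in fact late boosts. The persistent group in the LDL-C summaries could combine sustained treatment-induced responses with brief boosts on top of antibody that was present before dosing.

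**Working it through.** The plan gives no figure to reproduce, so the check applies its definitions literally.

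**Inputs**
- Cut-offs from SAP 8.2.4.1.1: ADA titer of at least 6.23 (2^6.23 ≈ 75) and a rise of more than 1.58 (2^1.58 ≈ 2.99, about 3-fold).
- ADA sampling at Visits 6, 8, 10, 12 and 14, that is Weeks 4, 14, 40, 70 and 104 (Protocol 6.4.2 to 6.4.4).
- Assumptions: onset uses post-dose samples, and the Week 104 sample falls more than 14 days after the last dose.

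Each post-dose sample is N (below the cut-off), P (positive, not boosted) or B (boosted), with at least one B. The rules as written count P and B. The comparison counts B only.

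| Weeks 4, 14, 40, 70, 104 | As written | Counting boosted samples only |
|---|---|---|
| PPPPB | Week 4, on, persistent | Week 104, off, indeterminate |
| PPPBB | Week 4, on, persistent | Week 70, on, persistent |
| BPPPP | Week 4, on, persistent | Week 4, on, transient |
| BBBBB | Week 4, on, persistent | Week 4, on, persistent |
| NNBBB | Week 40, on, persistent | Week 40, on, persistent |
| NNNNB | Week 104, off, indeterminate | Week 104, off, indeterminate |

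**Antibody detectable at every sample.** There are 2^5 − 1 = 31 patterns. As written, all 31 return Week 4, on-treatment, persistent. Counting boosted samples only:
- Onset changes when the Week 4 sample is P: 2^4 − 1 = 15 of 31.
- Duration changes when no run of boosted samples spans 16 weeks. The gaps between samples are 10, 26, 30 and 34 weeks, so any adjacent pair from Week 14 onward is enough for persistent. Of the 16 arrangements of the last four samples, 8 have no adjacent boosts. With two options at Week 4, and removing the pattern with no boost, 8 × 2 − 1 = 15 of 31.
- On/off changes only when the last sample is the sole boost: 1 of 31.

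**Antibody may fall below the cut-off.** There are 3^5 − 2^5 = 211 patterns.
- Onset changes in (81 − 16) + (27 − 8) + (9 − 4) + (3 − 2) = 90.
- Duration changes in 106, by enumeration.
- On/off changes in 2^4 − 1 = 15.

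These are counts of patterns, not expected frequencies.

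**Scale.** The documents give no rate of pre-existing ADA. As an assumption only, let 1–10% of treated subjects be positive at baseline and 10–50% of those be boosted. Against the 42.5% ADA incidence in Protocol 1.2.3, boosted subjects would be 0.01 × 0.1 / 0.425 = 0.24% to 0.10 × 0.5 / 0.425 = 11.8% of ADA-positive subjects. Those with an altered result are a subset of these.

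**The case against.** The strongest reply is that the gap is narrow and that several broader readings go too far. A reader might infer four things that the documents do not support.

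- **That every boosted subject gets a wrong value.** With antibody always detectable, onset is unchanged in 16 of 31 patterns and duration in 16 of 31. A subject boosted from the first post-dose sample onward is described correctly on all three.
- **That a boosted subject is always on-treatment and can never be off-treatment.** If antibody falls below the cut-off and returns only after treatment, the rule gives off-treatment. A boost seen during treatment is on-treatment under either reading. This part of the point is nearly empty.
- **That onset would be recorded at Day 1.** The SAP does not say that the baseline sample counts, and the subject-level and duration rules both look at samples after baseline. A post-dose reading is at least as natural.
- **That stable pre-existing antibody is filed as persistent.** A baseline-positive subject without a rise is ADA negative and gets no duration class.

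It can also be argued that continuous presence of antibody is a legitimate meaning of persistent, especially beside LDL-C. A rise-based duration rule could call a continuously positive subject transient because titers vary around a 3-fold threshold. That stands, and it is a reason not to rewrite the duration rule.

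Other outputs help: tabulation by response type, titers by visit, a listing with titer and induction type, and LDL-C by pre-existing ADA status and by titer tertile. They let a reader identify boosted subjects, but they do not correct the onset table or separate the two kinds of persistent subject.

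**Conclusion.** The point holds in a limited form. For treatment-boosted subjects the SAP applies the per-sample cut-off and leaves out the rise that made them positive. Where pre-existing antibody remains detectable, time to first positive is the first post-dose sample whatever the date of the boost. The persistent label, given at least 16 weeks of samples, then says nothing about how long the boost lasted. Onset is the clear fault. Duration is a matter of mixing two kinds of subject in one class. On/off timing fails only when the sole boosted sample is more than 14 days after the last dose.

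The conclusion assumes that onset is read from post-dose samples. The number of subjects affected cannot be stated from the documents. No hypothesis test, decision rule or primary result depends on these summaries, so this is a minor correction to descriptive immunogenicity and LDL-C output.

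**What to change.** - In SAP 8.2.4.1.1, state that time to first positive and on/off timing use post-dose samples only. For a subject who is ADA (nAb) positive at baseline, a sample counts for these two only if its titer exceeds the baseline titer by more than 1.58.
- Use the same date for days to first positive in the 8.2.4.2 listing.
- Leave the duration rule as it is. Report time to first positive, duration, and the 8.2.4.3 LDL-C summaries by duration separately for treatment-induced and treatment-boosted subjects.
- Align 5.4.2.5 and 8.2.3 with this text, and point their definitions to 8.2.4.1.1.

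The cost is a few sentences across these sections, one derivation change and some added table rows. The titers needed are already planned for analysis and listing, so no new data are required.
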